### **9.9.32. Activities of Daily Living**

Patients will be instructed to answer the 9 questions on the ADL survey at the times indicated in [Table 4](#) and [Table 5](#). The ADL survey ([Appendix 6](#)) assesses 9 concepts: (1) speech; (2) swallowing; (3) cutting food and handling utensils; (4) dressing; (5) personal hygiene; (6) falling; (7) walking; (8) quality of sitting position; and (9) bladder function.

### **9.9.33. Patient Global Impression of Change**

The Patient Global Impression of Change is a 7-point scale that requires the patient to assess how much the patient's illness has improved or worsened relative to a baseline state at the beginning of an intervention ([Guy, 1976](#)). Patients will be instructed to complete the Patient Global Impression of Change survey at the times indicated in [Table 4](#). The patient global impression of change is assessed by completing the following statement “since I began trial treatment, my overall status is: very much improved (1), much improved (2), minimally improved (3), no change (4), minimally worse (5), much worse (6), very much worse (7).” Patients must complete this assessment following completion of the FARS neurological assessment or the clinical global impression of change.

### **9.9.34. Clinical Global Impression of Change**

The Clinical Global Impression of Change is a 7-point scale that requires the clinician to assess how much the patient's illness has improved or worsened relative to a baseline state at the beginning of an intervention ([Guy, 1976](#)). Clinicians will be instructed to complete the Clinician Global Impression of Change survey at the times indicated in [Table 4](#). The clinician global impression of change is assessed by completing the following statement “Compared to the patient’s condition at the start of the trial, this patient’s overall status is: very much improved (1), much improved (2), minimally improved (3), no change (4), minimally worse (5), much worse (6), very much worse (7).” Clinicians may take into account prior results of study assessments to influence their clinical judgement of the Clinician Global Impression of Change. Clinicians must complete this assessment following the patient’s completion of the FARS neurological assessment or the patient global impression of change.

### **9.9.35. Falls Diary**

Throughout Part 2 of the study, patients will be instructed to record any instances of falls in a study diary ([Table 4](#)). A fall is defined as “the patient unintentionally coming to rest on the ground or at a lower level.” Items included on the falls diary may include but are not limited to the date and time of each fall, the location of the fall, the preceding activity prior to the fall, the perceived cause of the fall, and if an injury was sustained after the fall. Patients will be provided the fall diary at Screening and must record fall incidents between Screening and Week 48.

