### **6.2.3. Exploratory Objectives**

- To evaluate the distribution of change in mFARS scores at Week 48
- To evaluate the change in SF-36 score
- To evaluate the change in performance on a 9-HPT
- To evaluate the change in performance on a 25-foot timed walk test
- To evaluate the change in the Activities of Daily Living (ADL) score
- To evaluate the frequency of falls
- To characterize the PK of RTA 408 and potential metabolites after oral administration of RTA 408 Capsules

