## **8. SELECTION AND WITHDRAWAL OF PATIENTS**

### **8.1. Patient Inclusion Criteria (Part 1 and Part 2)**

Patients must:

1. Have genetically confirmed Friedreich's ataxia
2. Have an mFARS score  $\geq 20$  and  $\leq 80$ . The average of the two mFARS values collected at Screening and Day 1 visits must fall within the allowable range, and they must be within 4.5 points of each other
3. Be male or female and  $\geq 16$  years of age and  $\leq 40$  years of age
4. Have no changes to their exercise regimen within 30 days prior to Study Day 1 and be willing to remain on the same exercise regimen during the study period
5. Have the ability to complete maximal exercise testing
6. Have adequate kidney function defined as an estimated glomerular filtration rate (eGFR)  $\geq 60$  mL/min/1.73 m^2 using the Modification of Diet in Renal Disease (MDRD) 4-variable formula
7. Have a left ventricular ejection fraction  $\geq 40\%$  (based on echocardiogram performed at Screening Visit or within 90 days prior to Screening Visit)
8. Be able to swallow capsules
9. Be willing and able to cooperate with all aspects of the protocol
10. Be willing to practice medically acceptable methods of birth control (Section 9.7.2)
11. Provide written informed consent for study participation, approved by the appropriate Institutional Review Board (IRB)

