#### **9.9.29. 25-Foot Timed Walk Test**

Ambulatory patients will complete the 25-foot timed walk test at the times indicated in [Table 3](#), [Table 4](#), and [Table 5](#). If a patient uses an assistive device for the 25-foot timed walk test on Day 1, the same assistive device must be used for all 25-foot walk assessments. Patients will have the option to consent to video recording during the 25-foot timed walk test at selected sites. Video recording for the 25-foot timed walk test is optional. Procedures for video collection will be described in a separate study-specific manual.

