**11.2.9. Frequency of Falls**

The frequency of falls from Screening through Week 48 will be analyzed.

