**6. Falling (assistive device = score 3)**

- 0- Normal.
- 1- Rare falling (< once a month).
- 2- Occasional falls (once a week to once a month).
- 3- Falls multiple times a week or requires device to prevent falls.
- 4- Unable to stand or walk.

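### The protocol sets no at-risk population for the Part 2 falls endpoint and no rule for patients who are, or become, unable to walk, so fewer falls need not mean benefit

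*Protocol*

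**What the plan says.** Section 9.9.35 gives the falls diary to every Part 2 patient: "Throughout Part 2 of the study, patients will be instructed to record any instances of falls in a study diary". A fall is defined as "the patient unintentionally coming to rest on the ground or at a lower level", so being on foot is not part of the definition. On timing, "Patients will be provided the fall diary at Screening and must record fall incidents between Screening and Week 48". Table 4 allows Screening from Day -60 to Day -1.

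The only analysis statement is in Section 11.2.9: "The frequency of falls from Screening through Week 48 will be analyzed". It names no population, denominator, baseline adjustment or rule for loss of walking. The nearest default is Section 14.3.2, which bases the primary analysis of efficacy data on the ITT population. Section 6.2.3 lists falls as an exploratory objective ("To evaluate the frequency of falls").

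Entry does not require walking. Section 8.1 asks that patients "Have the ability to complete maximal exercise testing", and Section 9.9.26 puts that test on a recumbent bicycle. The mFARS must lie between 20 and 80.

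Elsewhere the protocol does take walking ability into account. In Section 9.9.29, "Ambulatory patients will complete the 25-foot timed walk test". In Appendix 6, item 6 (Falling), the worst score of 4 goes to "Unable to stand or walk", one step beyond falling several times a week or needing a device (score 3).

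**The concern.** Loss of walking is part of the natural course of this disease. Section 5.1 puts onset mostly before age 15 and wheelchair use a mean of 11 to 14 years later, so the transition can fall within the eligible ages of 16 to 40.

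A patient on foot is exposed to falls while standing and walking. Once walking is lost that exposure ends, though falls from a chair or during a transfer remain possible. If the net effect is fewer falls, the count drops as the patient gets worse, while ADL item 6 for the same patient rises to its maximum. Two measures of the same concept in one trial could then move in opposite directions.

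A treatment that keeps patients walking would keep them exposed and could show a higher fall rate than placebo for that reason alone. A larger sample would not remove this. Separately, counting from Screening mixes falls before the first dose into a comparison of treatments.

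**Working it through.** The documents give no fall rate, no rate of loss of walking and no power figure for falls, so there is no stated figure to reproduce.

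**1. Can a patient who cannot walk be enrolled?** From the item scales in Appendix 3:
- mFARS maximum = bulbar 11 + upper limb 36 + lower limb 16 + upright stability 36 = 99.
- A patient who cannot stand or walk but sits normally scores, on upright stability, six stance items at 4, tandem walk at 3 and gait at 5: 6 × 4 + 3 + 5 = 32.
- That is above 20 and leaves 80 − 32 = 48 points for the other sections. Such patients fit the entry range.

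**2. How large could the bias be?** Let L be the share losing walking in each arm, f the share of follow-up after the loss, and k the fall rate after the loss relative to before. With no other treatment effect,

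rate ratio (active/placebo) = (1 − L_active × f × (1 − k)) / (1 − L_placebo × f × (1 − k)).

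L, f and k are all assumptions.

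| Loss, placebo / active | f | k = 0 (falls stop) | k = 0.5 (falls halve) | k = 1 (unchanged) |
|---|---|---|---|---|
| 5% / 0% | 0.25 | 1.013 | 1.006 | 1.000 |
| 5% / 0% | 0.50 | 1.026 | 1.013 | 1.000 |
| 10% / 5% | 0.25 | 1.013 | 1.006 | 1.000 |
| 10% / 5% | 0.50 | 1.026 | 1.013 | 1.000 |
| 15% / 5% | 0.25 | 1.026 | 1.013 | 1.000 |
| 15% / 5% | 0.50 | 1.054 | 1.026 | 1.000 |

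Example, last row with k = 0: (1 − 0.05 × 0.5)/(1 − 0.15 × 0.5) = 0.975/0.925 = 1.054. For any k below 1 the ratio exceeds 1, which counts against the arm that preserves walking.

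**3. Are those losses plausible?** The one relevant figure in the protocol is the mean of 11 to 14 years from onset to wheelchair use (Section 5.1). Read crudely as a constant rate, it gives (48/52)/14 = 6.6% to (48/52)/11 = 8.4% over 48 weeks. If the drug prevented every loss and falls then stopped, with f = 0.5, the ratio is 1/(1 − 0.5 × 0.066) = 1.03 to 1/(1 − 0.5 × 0.084) = 1.04. That sits inside the table. Patients later in the disease could lose walking faster.

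**4. The pre-dose window.** With the full 60-day Screening period and 336 days of treatment, 60/396 = 15% of the counted time precedes the first dose. If the daily placebo rate is constant, a true on-treatment ratio R appears as (60 + 336R)/396. Only 336/396 = 85% of its distance from 1 remains.

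**The case against.** The strongest points on the other side are these.

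- **The main Part 2 SAP is not among the documents.** The SAP document available is a short note on sparse sites, and Section 14.3 makes the SAP the final arbiter. A falls population or a rule for loss of walking may be set there. This stands: the gap can be asserted for the protocol only.
- **Patients who lose walking need not stop falling.** A reader might infer that they do, and that the trial would score them as improved. The documents support neither. The definition in Section 9.9.35 includes falls from a chair or transfer, and no change score, responder rule or ranking for falls exists. What remains is conditional: if falls become less frequent, a lower count can reflect decline.
- **Larger effects depend on unsourced inputs.** Assumed losses of 5% against 20%, or 10% against 30%, with f = 0.5 and no falls afterwards, would give 0.975/0.90 = 1.08 or 0.95/0.85 = 1.12. Placebo losses of that size exceed the 7% to 8% implied by the protocol's own figure. A claim that non-ambulatory patients materially inflate the variance also needs a fall mean, a dispersion and a near-zero count in those patients, none of which the documents give.
- **Loss of walking is captured elsewhere,** in the mFARS gait item and in ADL items 6 and 7. True, but that does not make the falls result itself interpretable.
- **Ranking loss of walking as the worst outcome is one estimand choice among several,** and it largely repeats ADL item 6. This stands, and it is why that analysis is proposed only as a sensitivity analysis.
- **The stakes are low.** Falls is one of seven exploratory objectives and is missing from the Part 2 efficacy variables in Section 14.2.3. This limits the importance of the point but does not answer it.

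**Conclusion.** The concern holds in a limited form. The protocol collects falls from all Part 2 patients and plans to analyse their frequency without an at-risk population or a rule for patients who are, or become, unable to walk, although they are eligible. A reduction in falls therefore cannot be read as benefit, nor a rise as harm, without knowing who was still walking.

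The bias is probably small: an illustrative rate ratio of 1.01 to 1.05 under no true effect if falls stop after walking is lost, about 1.01 to 1.03 if they halve, and none if the rate is unchanged. It would reverse if falls became more frequent after the loss. All of this rests on assumed losses of walking, since the documents give none. The pre-dose window is a separate defect, diluting any on-treatment effect by up to 15% when Screening lasts the full 60 days.

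The primary endpoint is untouched. The change is still worth making because it costs little and makes an exploratory result interpretable.

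**What to change.** If the main Part 2 SAP does not already do so, specify the following.

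- **Main falls comparison:** falls from Day 1 to Week 48 in patients ambulatory on Day 1, defined as a FARS gait item below 5. Falls between Screening and Day 1 can serve as a baseline covariate, expressed per day because the length of Screening varies.
- **Descriptive reporting:** fall rates in all patients by ambulatory status, and the number in each arm who lose walking ability.
- **Sensitivity analysis:** ordered categories of fall frequency with loss of walking as the worst category, following the order of ADL item 6.

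The cost is analysis wording for an exploratory endpoint. Table 4 schedules the FARS on Day 1 and at Weeks 4, 12, 18, 24, 36 and 48, so loss of walking can be placed within at most 12 weeks. Section 9.9.35 names date and time among the items the diary may record; the sponsor should confirm that dates were captured. The small downside is that falls in patients non-ambulatory on Day 1 are reported descriptively only.

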**9.9.36. Pharmacokinetic Analysis (Part 1 and Part 2)**

Blood samples for plasma PK analysis will be collected at the times indicated in [Table 3](#) and [Table 4](#). Blood sample collection instructions are detailed in the lab manual. All pre-dose blood samples should be collected within 1 hour prior to dose administration. All other blood samples for PK analysis should be collected  $\pm$  15 minutes of the scheduled time.

The date and time of collection of all PK blood samples should be recorded; however, any deviations from the protocol-specified sampling times will not be considered protocol deviations. Sample time deviations will be summarized in the study report. Dates in the CRF should be recorded in an unambiguous format (e.g., DD MM YYYY) and time should be recorded to the nearest minute (e.g., HH:MM using the 24-hour clock). Blood samples not collected should be recorded as such. Detailed sample processing instructions will be provided for isolation, storage, and shipment of plasma PK samples.

**9.9.37. Home Health Visits**

For part 1 and part 2 patients at approved sites will have the option of having a home health visit at the Screening Visit (all patients, Part 1 and Part 2) and Visit 3 (Part 1 only).

[figure not shown]
During the extension every effort should be made to ensure patient assessments are performed on-site. If this is not possible, home health visits are acceptable. For more detail regarding use of home health services see [Appendix 13](#) (COVID-19 Mitigations).

**9.9.38. Low-Contrast Letter Visual Acuity Test (Part 1 Only)**

The low-contrast letter visual acuity test will be performed at the times indicated in [Table 3](#) ([Appendix 7](#)). Instructions are provided in the study manual. Low-contrast letter visual acuity parameters include but are not limited to the number of letters that the patient correctly identifies for each line, the letters the patient missed on each line, contrast level (100%, 2.5%, or 1.25%), chart number, and if the assessments were performed in both eyes or 1 eye. If a patient uses standard vision correction on Day 1, the same vision correction must be used for all low-contrast letter visual acuity assessments. Different charts should be used on different days for each patient.

**9.9.39. Fatigue Severity Scale (Part 1 Only)**

Patients will be instructed to answer the 9 questions on the Fatigue Severity Scale ([Krupp, 1989](#)) at the times indicated in [Table 3](#). They will answer according to a recall period over the past week. Patients will assign a number from 1 to 7 that indicates their degree of agreement with each statement (where 1 indicates strong disagreement and 7 indicates strong agreement; [Appendix 10](#)).

**9.9.40.**   

[REDACTED]

[REDACTED]

[REDACTED]

[REDACTED]

[REDACTED]

**9.9.43. Platelet Collection (Part 1 Only)**

Platelet collection will be required only at Sponsor-qualified sites. Blood samples for platelet analysis will be collected at the times indicated in Table 3. Blood samples (8.5 mL each) will be collected into 8.5-mL acid-citrate-dextrose Vacutainer® tubes. Procedures for platelet isolation and analysis will be provided in a study manual.

## 10. STUDY DRUG MATERIALS AND MANAGEMENT

### 10.1. Study Drug

Capsules containing RTA 408 at the 2.5-mg, 10-mg, and 50-mg strengths, or the corresponding placebos, as described in Table 9 will be used in this study.

**Table 9: Study Drug Information**

Description	RTA 408 Capsule, 2.5 mg, 10 mg, 50 mg	Matching Placebo Capsules
Ingredients	RTA 408, silicified microcrystalline cellulose, pregelatinized starch, croscarmellose sodium, magnesium stearate, in white opaque, size #4 or #0 capsule shells consisting of hypromellose and titanium dioxide	Silicified microcrystalline cellulose, pregelatinized starch, magnesium stearate, in white opaque, size #4 or #0 capsule shells consisting of hypromellose and titanium dioxide

### 10.2. Study Drug Packaging and Labeling

RTA 408 active and placebo capsules are contained in identical primary container closure systems (i.e., 75-cc high-density polyethylene bottles with a foil induction-seal liner and a child-resistant closure). Treatment kits containing three, four, or six bottles, depending on treatment assignment, will be provided to patients for self-administration. Each bottle will contain 30 capsules and a desiccant insert that must not be ingested. The label on each bottle will include the following information:

- Protocol 408-C-1402
- Medication ID number
- Caution statement: New Drug – Limited by Federal Law to Investigational Use (United States [US])
- Storage: Controlled room temperature, 20°C to 25°C (68°C to 77°C), with excursions allowed between 15°C and 30°C (59°C to 86°C)
- Sponsor name, address, and contact information
- Contents: One bottle containing 30 capsules of either RTA 408 or matching placebo. Bottle also contains one desiccant insert, which should not be ingested
- Directions for use: Take capsule as directed, orally, once daily in the morning on an empty stomach (1 hour before or 2 hours after eating) with water
- Keep out of sight and reach of children
- FOR ORAL USE ONLY

Additionally, expiry information will be provided on treatment kits intended for use in the European Union (EU).

### **10.3. Study Drug Storage**

The stability of the drug product is being evaluated in ongoing studies.

Investigative sites must store the investigational product in a secure location under controlled room temperature conditions of 20°C to 25°C (68°F to 77°F), with excursions allowed between 15°C and 30°C (59°F to 86°F). Sites must maintain a temperature log of the storage conditions. Temperature logs must be available for review at each monitor site visit. If a temperature within the storage location at the site is noted to be outside the excursion range for 24 hours or more or exceeds 40°C, the Sponsor must be notified.

### **10.4. Study Drug Administration**

Please refer to Section 9.9.24 for details on study drug administration. Patients will receive enough capsules for continuous dosing once daily at least until the next study visit. Clear instructions will be provided to the patient regarding study drug administration for each study drug administration time point listed in Table 3, Table 4, and Table 5.

### **10.5. Study Drug Accountability**

The investigator or designee will maintain a record of all study drug received, dispensed, and returned to the Sponsor or its designee. No study drug shall be destroyed by the clinical site unless directed to do so by the Sponsor or its designee. Study drug bottles and any unused capsules should be returned by the patient to the study staff.

### **10.6. Study Drug Handling and Disposal**

At the conclusion of the study, the Sponsor or its designee will direct the site regarding the final disposition of any remaining study drug.

## **11. EFFICACY ASSESSMENTS**

### **11.1. Part 1**

#### **11.1.1. Maximal Exercise Test**

The changes in peak work and oxygen utilization during maximal exercise testing from Baseline to Weeks 4 and 12 will be analyzed.

#### **11.1.2. Friedreich's Ataxia Rating Scale**

The change in both the FARS neurological score and the mFARS scores from Baseline to Weeks 4, 8, and 12 will be analyzed.

#### **11.1.3. 25-Foot Timed Walk Test**

The change in 25-foot timed walk test distance from Baseline to Weeks 4, 8, and 12 will be analyzed.

#### **11.1.4. Low-Contrast Letter Visual Acuity Test**

The change in performance on the low-contrast letter visual acuity test from Baseline to Weeks 4, 8, and 12 will be analyzed.

#### **11.1.5. 9-Hole Peg Test**

The change in performance on the 9-HPT from Baseline to Weeks 4, 8, and 12 will be analyzed.

#### **11.1.6. Fatigue Severity Scale**

The change in Fatigue Severity Scale patient-reported outcome scores from Baseline to Week 12 will be analyzed.

#### **11.1.7. SF-36 Health Survey Update**

The change in SF-36 patient-reported outcome scores from Baseline to Week 12 will be analyzed.

[REDACTED]

### **11.2. Part 2**

#### **11.2.1. Friedreich's Ataxia Rating Scale**

The change in both the FARS neurological score and the mFARS scores from Baseline to Weeks 4, 12, 18, 24, 36, and 48 will be analyzed.

**11.2.2. Patient Global Impression of Change**

The proportion of patients who are a treatment success at Weeks 12, 24, 36, and 48, based on the Patient Global Impression of Change. A treatment success is defined as “Much Improved” or “Very Much Improved” on the Patient Global Impression of Change.

**11.2.3. Clinical Global Impression of Change**

The proportion of patients who are a treatment success at Weeks 12, 24, 36, and 48, based on the Clinical Global Impression of Change. A treatment success is defined as “Much Improved” or “Very Much Improved” on the Clinical Global Impression of Change.

**11.2.4. Maximal Exercise Test**

The changes in peak work and oxygen utilization during maximal exercise testing from Baseline to Weeks 4, 12, 18, 24, 36, and 48 will be analyzed.

**11.2.5. 9-Hole Peg Test**

The change in performance on the 9-HPT from Baseline at Weeks 24 and 48 will be analyzed.

**11.2.6. 25-Foot Timed Walk Test**

The change in performance on the 25-foot timed walk test from Baseline at Weeks 24 and 48 will be analyzed

**11.2.7. SF-36 Health Survey Update**

The change in SF-36 patient-reported outcome scores from Baseline at Weeks 24 and 48 will be analyzed.

